7.1.2 Screening

Participants will be screened by a purpose-built website programmed within Qualtrics by University of Exeter and those under 16 and over 22 will automatically be screened out pre-assessment. Those aged 16/17 who live outside of the UK and Spain will require parental permission to take part in the trial and will automatically be taken to a separate page on the screen. On this page they will be asked to complete their parent's contact details and the parent will be sent a link to give parental permission on Qualtrics. After parental permission has been collected, an email will be sent to the participant providing them with a link to return to the survey at the point of consent A. Website users who report having current risk will be taken to the feedback screen where they will be advised that we are sorry to hear that they are feeling that way, to please contact their GP and to give them sources of online help and support. For those with current depression that are not indicating risk we will provide information on where to get help for symptoms of depression and advise that they contact their GP.

7.1.3 Payment

Participants will be paid in electronic shopping vouchers or equivalent for taking part in the three follow up assessments; we will pay 10 euros/pounds for completing each of the 3 follow ups. Participants will also be able to gain badges that they can exchange for rewards through the gamification system of the App. The gamification system on the app will reward the earning of badges at different levels (complete all available badges at bronze earn 10 euros/pounds, complete all at silver earn 10 pounds/euros; complete all at gold earn 10 pounds/euros). The maximum honorarium a participant can gain for using the App is 30 euros/pounds, so the participant can earn up to a maximum of 60 pounds for taking part in the study. European participants will be paid in Euros.

MSS will transfer information on the number of badges earnt to the EXCTU system where it can be linked with the completion of follow ups and the appropriate amount paid in vouchers. Researchers will be able to run reports on the EXCTU database to identify which participants have earnt badges and completed follow ups at the key payment points (after 3month and 12month follow ups). Site researchers will arrange for the payment of participant using electronic shopping vouchers (or equivalent) which can be emailed or sent by text. An automated system of voucher will be created (if possible). No travel expenses are anticipated for participants as all assessment and intervention contents are provided remotely via digital platforms (website, app).

7.2 Consent

We distinguish between autonomous independent young adults who are legally recognized as being at or above the age of majority and able to provide their own informed consent to their participation in research (age of majority is aged 16 or over for the UK and Spain and 18 or over for Germany and Belgium) versus those adolescents and young adults who are below the age of majority in their respective country, and for whom both their own informed assent and permission from their parents or legal guardian (dependent on nation and jurisdiction) is necessary for their participation.

See section 7.1.2 for more information on the parental permission process.

Participants aged 16/17 from Belgium and Germany will not be able to take part until a signed parental permission form has been received by the site.

Obtaining informed consent for those above the respective age of majority for the country of recruitment will be a two-stage process. For those who need parental permission there will be a pre-consent process to obtain parental permission first. Then there will be the same process described below of providing consent to undertake the assessment and then providing consent to take part in the study is followed.

Young people will be initially routed to or seek out the study website and after age screening will be provided with the participant information sheet (which will be submitted with the protocol), consent form A and data protection policy to review on the screening website. There will be a check box at the bottom of the information sheet which participants will need to check before they can sign the consent form. Participants will then be asked to read, date and electronically sign consent form A and provide their contact details. Consent form A asks for consent to undertake the assessment and confirmation that the participation understands the nature of the study (the consent forms will be submitted for review with this protocol). When consent is given they will automatically be emailed a copy of the consent form, information sheet and data protection /privacy policy. The recruit will then be asked to complete background screening measures to determine eligibility on the online screening website. Non-excluded recruits can stop and save their assessment at any time and be emailed a link to return to the assessment. The participant will have 2 weeks in which to be able to return to their part completed assessment. After this time they would need to start the assessment again if they wanted to take part.

If a participant completes the baseline assessment and is eligible for the cohort and trial then they will be presented with consent form B which asks them to consent to taking part in the trial. Recruits are advised that they can take time to consider taking part and can save their assessment whilst they do so. Our Youth Advisory Board advised us that most recruits would probably want to continue and gain access to their App at this stage and would be discouraged by having to wait. There is therefore an option for the participants to consent to take part in the cohort/trial at the end of the assessment. On completion of consent form B participants are advised that our App developer MSS will be emailing them a link to access their App and when their next follow up is due. At this stage the recruit is randomised and be given a unique participant trial number.

All participants will be given the option to seek further information from the research team, with contact details to the relevant (national) research team provided (email, and/or telephone number for each recruitment site, as available). This information will be provided on all versions of the information sheet and on the help menu of the app and screening website.

Our proposed procedures for recruiting and screening young people into the cohort have previously been approved by local and national ethics committees, and we will obtain approval before commencing the study. In all centres, each PI who is recruiting participants for the prospective cohort will ensure that the necessary arrangements for agreement to access and use of data are respected by researchers and site training will be provided by the trial manager. The sponsor will take out civil liability insurance to protect participants.

7.2.1 Additional consent provisions for collection and use of participant voice recordings

The option to voice record a diary record will be possible in the emotion diary part of the App. This function will be available in all versions of the app and all trial conditions This option is described in the information sheet and the privacy and data protection policy. The participant is also explicitly asked to confirm that they know there is the option to voice record. Participant would have to press record for this function to become active.

7.3 The randomisation scheme

Random selection to the 3 arms (offering EC self-help app; offering CBT self-help app; or continuing with self-monitoring app alone – usual practice) will be conducted automatically by means of a secure web service created and managed by the Exeter Clinical Trials Unit (CTU) in conjunction with the trial statistician. This will be independent of the trial researchers. To promote balance across key participant characteristics across groups, we will minimize allocation by sex, country from which participant is entering the trial (reflecting trial site; i.e., UK; Spain, Germany, Belgium), and age (16-17 vs. 18-22 years). We split the sample into two age ranges to reflect naturally occurring transitions (e.g., between secondary education vs. tertiary education; into the workforce) and that the concerns and issues of 16/17 year olds may differ from those of 18 to 22-year olds. To maintain concealment, the minimisation algorithm will retain a stochastic element and the first 50 participants will be allocated to each by simple random allocation.

Protection from bias

We will adopt prior registration and publication of the trial protocol. Independent web-based computerised randomisation will be conducted to ensure generation of an unpredictable allocation sequence and concealment of participant allocation and of allocation sequence and prevent selection bias and confounding. We will use standardised assessments with data collected automatically through the website. The use of self-administered measures will eliminate observer bias. A detailed statistical analyses plan will be prepared and agreed with Trial Steering Committee before any analysis is

conducted. The trial statistician will remain blinded to group allocation until the main data analyses have been undertaken and interpretation of the trial results have been agreed by the relevant committees. Attrition bias will be minimised by having robust trial procedures to prevent data loss such as email, text and phone reminders to encourage follow ups.

7.3.1 Method of implementing the randomisation/allocation sequence

Participants will be randomised by a custom-built web service which interfaces with the EXCTU database. This will be an automated process. The EXCTU database will send MSS the email address and the version of the App that the participant is randomised to. The participant will automatically be set up with an MSS account and this account number will be recorded and linked to the trial number. Once the MSS account has been set up, the participant will receive an automated email from MSS providing instructions on how to access their version of the App. In the unlikely case that it is necessary, site researchers will be able to log on to the EXCTU website to identify which condition the participant has been allocated so that they can give advice on any problems the participant has in using the App. If this happens then this will be logged as an unblinding. The functioning of the randomisation programme will be checked by the data team and reported to the DMEC.

Detailed procedure for randomisation

- 1. Participants are allocated to one of 2 trials within the cohort:
 - a. ECoWeB-PROMOTE (EC profile indicates low risk for emotional difficulties),
 - b. ECoWeB-PREVENT (EC profile indicates higher risk for emotional difficulties)

For each trial, participants are randomised on a 1:1:1 basis into the 3 arms on an intentionto-treat basis: usual practice plus offered personalized digital EC self-help (the experimental intervention), usual practice plus offered digital CBT self-help (active control) and continuing with usual practice including self-monitoring app (control). Gender, age and country are used for minimisation.

- 2. The system must record the allocation and the date randomised.
- 3. The participant and researcher remain blind to the allocation.
- 4. If the participant is randomised to the EC condition (in any of the trials) then the EC profile from step 5 will be used to tell Monsenso which version of the App to provide the participant with.
- 5. An algorithm (simple set of rules) will be provided to determine the version of the app received within the personalised EC configuration and the bespoke website will communicate this information to Monsenso. This will be based on trial, interventions and EC category.
- 6. The system notifies Monsenso of the allocation. They will need to be notified of the version of the app, trial no, participant language and participant email address.
- 7. On successful randomisation, a finish page is displayed with a message telling the participant to look for an email message from Monsenso.

7.4 Blinding

The follow up data will be routinely be collected online using the website (and the reminders for this will be sent out automatically by email from the screening website). This will prevent the follow up results being affected by the site researcher.

Site researchers will be blind to treatment allocation but will be in direct contact with participants to follow up risk and to answer technical queries. It is possible that a site researcher could become unblinded

during those (infrequent) conversations if the participant mentions details of their version of the App. Participants will need to have someone who speaks their language to ask about technical queries as lack of technical support has been found in other studies to increase attrition. The App host MSS cannot provide this support because their staff do not speak all 4 languages.

Should a site researcher become unblinded then this will be logged as an unblinding and any telephonebased chasing of follow up data for that participant in future will be conducted by another blinded researcher at the site (if available). Therefore, only blinded site researchers will attempt to collect the primary outcome measures by telephone if the participant is unwilling to use the screening website for this purpose. Unblinded site researchers will not discuss information relating to condition with blinded site researchers. During any contact with participants the blinded site researcher will remind them not to divulge to which version of the App they were allocated. In the event that there are no unblinded researcher at a site and telephone collection of follow up primary outcome is possible, this data will be collected, but will be logged and clearly marked as 'collected unblinded'. This will allow the statisticians to control for this in their analysis. The statisticians and the Steering Committee will be blinded to intervention until the analysis is done and they are interpreting the results.

7.5 Emergency Unblinding

It is extremely unlikely that a site researcher would need to be unblinded, even in cases of risk. The trial code would only need to be broken for valid medical or safety reasons, for example in the case of a serious adverse event, where it is necessary for the investigator or TSC (DMEC) to know whether there is a relationship between condition and adverse events. In these circumstances, the research team will remain blinded. Where a person raises clinical relevant concerns or reports risk, and where knowing the trial condition is relevant, one of the project team dealing with this participant can potentially be unblinded to the participant's condition to support their care and further support them – in many cases, it may not be necessary to know the app condition. The action taken according to the risk protocol would be the same, regardless of condition. The PI will be able to request the condition from the CTU if there are any adverse events. In the case of a serious adverse event, it will be necessary for principal investigator / site-relevant clinician to be unblinded for safety reasons and for accurate reporting onto the TSC/DMEC.

The TSC/DMEC will be unblinded in aggregate to cases of serious adverse events (i.e., knowing condition for those reporting serious adverse events, but no other personal information) in order to have an overview of the relationship between condition and risk.

7.6 Baseline data

The CRF for the collection of baseline is available as a separate appendix. These data will be collected after the screening section of the screening website. The measures used have been described previously in Section 3.

7.7 Trial assessments

Assessment will take place at baseline and then at 1, 3, and 12-months post randomisation. The 3month follow up will be the primary endpoint. All assessments will be through the survey website programmed in Qualtrics. Only if participants have not responded to email and text prompts to complete their follow ups at 3 or 12-months will they be contacted by phone and asked to provide the primary outcome measures only on the telephone. (We have found that in previous studies participants are often willing to provide these measures on the phone rather than complete the full online assessment). The results of the assessments are only to collect research data for the trial and will not be provided to medical practitioners. The only exception to that would be if a participant indicates suicide risk and asks us to provide their assessment results to their medical practitioner. They would need to give written consent for this and provide us with the contact details to do so. See risk protocol in Appendix 16.

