- The survey site programmed in Qualtrics will host the follow up assessments and the system will automatically email reminders to participants with a link to access the site so that they can complete follow ups at month 1, 3, and 12. The data will automatically be collected though the API and stored on the EXCTU database.
- The only data collections at sites would be by the site researcher on the telephone if the participant has not completed their follow up and is willing to complete the primary outcome measures only on the phone.

A flow diagram of how the data flow will work between EXCTU, MSS and AUD can be found on the following page:

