9.3 Recording and reporting of SAEs, SARs AND SUSARs

All serious adverse events that are trial or treatment related will be recorded and immediately reported to the Chief Investigator and within 2 working days to the trial sponsor. If these are also classed as unexpected they will be reported to the relevant ethics committees. We will, in line with other complex intervention studies, monitor non-serious adverse events, serious adverse events that are not trial or treatment related, serious deterioration, and active withdrawals from treatment, with specific questions in the follow-up and in response to specific participant-initiated reports. Symptoms of depression or anxiety will not be defined as adverse events unless suicidal ideation, plans or an attempt has been made. The reporting period for all events and reactions will be from referral to 12month post baseline follow-up. Data on any adverse events will be collected by a member of the research team at each assessment.

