9.4 Responsibilities

Researchers at each trial site to check for AEs and ARs when participants complete digital treatment / follow-up, potentially in response to automated feedback from website

- 1. Principal Investigator (PI) for each trial site is responsible via liaison with research team at trial site for: Ensuring that all SAEs are recorded and reported to the sponsor within 2 working days of becoming aware of the event and provide further follow-up information as soon as available. Ensuring that SAEs are chased with Sponsor if a record of receipt is not received within 2 working days of initial reporting.
- 2. Ensuring that AEs and ARs are recorded and reported to the sponsor in line with the requirements of the protocol.
- 3. Immediate review of all SUSARs.
- 4. Review of specific SAEs and SARs in accordance with the trial risk assessment and protocol as detailed in the Trial Monitoring Plan.

Sponsor (NB where relevant these can be delegated to CI and trial manager)

- 1. Central data collection and verification of AEs, ARs, SAEs, SARs and SUSARs according to the trial protocol onto a database.
- 2. Reporting safety information to the CI, delegate or independent clinical reviewer for the ongoing assessment of the risk / benefit according to the Trial Monitoring Plan.
- 3. Reporting safety information to the independent oversight committees identified for the trial (Data Monitoring Ethics Committee (DMEC) and / or Trial Steering Committee (TSC)) according to the Trial Monitoring Plan.
- 4. Expedited reporting of SUSARs to the Competent Authority (MHRA in UK) and REC within required timelines.
- 5. Notifying Investigators of SUSARs that occur within the trial.
- 6. Preparing standard tables and other relevant information in collaboration with the CI and ensuring timely submission to the MHRA and REC.

Trial Steering Committee

In accordance with the Trial Terms of Reference for the TSC periodically reviewing overall safety data to determine patterns and trends of events, or to identify safety issues, which would not be apparent on an individual case basis.

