16.5 Safety Reporting Flow Chart

Safety Flow Chart Version 1

AE reported on screener follow up. CTU website logs all AE and reported reasons

Website sends alert to site PI, site researcher and trial manager if AE reported and ppt ticks that its related to trial participation AE reported to site Researcher via email or phone, Risk log to be completed and submitted to site PI within 2 days.

AE Monitoring

All sites to produce end of monthly report of AE/SAE, unblindings and protocol violations to trial manager

Site researcher attempts to contact ppt within 2 days to find out more if insufficient data to complete risk log

Trial manager to review site reports and CTU websites log of AE/SAE at the end of every month and provide monthly report for CI and DMEC representative /

If SAE reported to site Researcher via email or phone or website alert Risk log to be completed (contacting ppt if necessary) and submitted to site PI, trial manager and CI within 2 working days.

> If SAE reported to CI TM/CI informs the sponsor, steering committee and DMEC within 2 working days of event being reported

If serious concerns for patient wellbeing/scientific rigor then discussion with ethics committee within 7 days of event being reported

SAE check-AE questions to be asked at follow up, or if reported to the site researcher by phone/email: Have you experienced any health emergencies, accidents, unplanned hospital admissions in the last 3 months? What happened? (please describe) What caused this? Please tick all that apply Sports injury Traffic accident Assault Self injury Taking part in the trial Physical illness Work Other please state

AE check-Overall, has taking part in the trial so far made you feel much worse.....no effect.....much better? Please give details Have you had any problems with the App. If yes please give details:

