## 3.9 Allocation masking

Participants will not be specifically informed of their treatment allocation. Participants will be informed prior to consenting to participate that they may be randomly selected to receive additional support and education in mental health and wellbeing via the app. Therefore, it is reasonable to assume that participants allocated to the usual care intervention who do not receive any support or information vie the app will be able to deduce that they are in a control arm, although this should be mitigated to some extent by the cohort trial design. Similarly, participants allocated to either of the two active interventions will be aware that they have been selected to receive additional support and education, and may be able to determine whether they are in the personalised intervention arm or the standard intervention arm. The issue of differential participant awareness of intervention arm will be considered when interpreting the results.

All outcome data is participant reported and will be collected via the website with no direct contact between participants and researchers. Contact between a participant and researcher would only occur if the researcher's support is required for concerns about risk of harm to the participant or for technical support with use of the app or as an additional attempt to obtain primary outcome data. Thus, there is the possibility for inadvertent unblinding of the researcher if such contact occurs. Any cases of researcher unblinding will be logged. There is provision for data collection to be conducted by telephone if a participant is unwilling or unable to use the website; such instances are anticipated to be rare, and in such cases, data collection will be performed by a blinded researcher. Data collected by telephone (as opposed to via the website, which is standard) will be recorded as such. There may be extremely rare instances where data collection by telephone is performed by an unblinded researcher, and such cases will be recorded as such.

Following database lock on completion of 3-month data collection, the database will be made available to the trial statistician with masked treatment allocation. The final database with completed 12-month follow-up data will be made available to the trial statistician following database lock; at this point the trial statistician will be aware of allocations.

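### As written, the telephone follow-up at 3 and 12 months collects only the primary outcome measures, so it omits the SAE question that the protocol schedules at every follow-up (minor)

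*Protocol*

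**What the plan says.** Two places in the protocol limit what the call collects. Section 7.7 says that people who have not responded to email and text prompts at 3 or 12 months will be "contacted by phone and asked to provide the primary outcome measures only on the telephone". Section 7 describes the same call as being for a participant who is "willing to complete the primary outcome measures only on the phone".

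Two other places describe the call without limiting its content. In Protocol 7.4, "only blinded site researchers will attempt to collect the primary outcome measures by telephone", the word *only* governs who may call. SAP 3.9 gives one reason for contact, "as an additional attempt to obtain primary outcome data". It separately allows telephone collection for people who cannot or will not use the website, with no list of contents, and remarks that "such instances are anticipated to be rare".

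On safety, Protocol 9.3 states: "Data on any adverse events will be collected by a member of the research team at each assessment". The schedule in 16.4 marks adverse-event assessment at 1, 3 and 12 months. Section 9.4 has site researchers "check for AEs and ARs when participants complete digital treatment / follow-up". The flow chart in 16.5 starts from "AE reported on screener follow up. CTU website logs all AE and reported reasons", with a second route for events that a participant reports by phone or email. It also gives the SAE question, on health emergencies, accidents and unplanned admissions in the last 3 months, with self-injury among the listed causes.

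SAP 6.10 names deliberate self-harm as the main anticipated event. It analyses both the count of serious events and the number of participants with at least one over 12 months, using observed data.

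**The concern.** A telephone completer supplies a primary outcome but, on the written plan, is never asked whether a serious event has occurred. A researcher who follows 7.7 omits a question that 9.3 and 16.4 require, and one who follows 9.3 goes beyond 7.7. The text gives no rule for choosing.

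What is at stake is the completeness of the counts in SAP 6.10. That section does not say how a participant who was never asked is handled, so such a person could be counted as event-free. The contact is already being made, and it is the one follow-up mode in which a researcher speaks to the participant.

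**Working it through.** **Side by side**

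| Place | What it fixes |
|---|---|
| Protocol 7, 7.7 | Content of the call: primary outcome measures only |
| Protocol 7.4 | Who may call |
| SAP 3.9 | A purpose of the call; no limit on content |
| Protocol 9.3, 16.4 | Adverse-event collection at each follow-up; no telephone exception |
| Protocol 16.5 | SAE question at follow-up, or when an event is reported by phone or email |

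The primary measures are WEMWBS and PHQ-9 (Protocol 10.3.2). Neither contains the SAE question, and no section adds it to the call.

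**Does PHQ-9 item 9 fill the gap?** Only in part. It asks about thoughts in the last two weeks (Protocol 16.1), not past events. A positive answer could lead to the telephone risk procedure in 16.1, which asks about past attempts. Someone admitted for self-injury some months earlier, with no current thoughts, would be recorded only if they volunteered it. The documents also do not say whether PROMOTE participants are asked the PHQ-9 by phone: Table 13 lists both measures as primary, while 10.3.2 assigns one to each trial.

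**Months the SAE question would add.** Inputs: a 3-month look-back (Protocol 16.5), and the 1-month follow-up assumed done online.
- Call at 3 months: 3 − 1 = 2 months.
- Call at 12 months: months 9 to 12, so 12 − 9 = 3 months.
- Both by phone: 2 + 3 = 5 months.

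The look-back at 12 months does not reach months 3 to 9 in either mode. Online, the AD-SUS covers hospital and emergency care since the 3-month interview (Protocol 3.3), that is 12 − 3 = 9 months. With the SAE question alone, a telephone completer at 12 months would still lack 9 − 3 = 6 of those months.

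**How many people.** The number of calls is not stated and cannot be derived. For scale only: with the revised target of 3599 (SAP 6.9) and the 40% loss allowed for at 3 months (SAP 3.4), completers number 0.60 × 3599 = 2159. Each percentage point of completers reached by phone would be about 0.01 × 2159 = 22 people. Those giving no 3-month data would number 0.40 × 3599 = 1440.

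**Whom a change could still reach.** SAP 6.9 Groups 1 to 3 registered before 10 March 2021: 446 + 465 + 992 = 1903 of 2141. Their 3-month dates fell by about 10 June 2021, and the 14 days allowed after the scheduled date (SAP 3.8) ended by about 24 June. Both precede the protocol date of 05/07/2021 (SAP 1.4). The other 238 signed up after 25 March, and some of them may also have been past 3 months by then.

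**The case against.** The best defence is that *only* in 7.7 sets the questionnaire burden, since that section contrasts these measures with the full online assessment. The duty in 9.3 would then stand on its own and apply to any call. Alternatively, the call is a salvage contact after a missed assessment, so the schedule in 16.4 does not attach to it. Either reading would remove the conflict, but neither is in the text, and a caller could reasonably follow either section. The telephone script is not in the documents, so the point concerns the written plan and not what callers actually asked.

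Three parts of the defence stand. The short call is a deliberate choice to rescue primary data, and adding AD-SUS items would work against it. Other capture remains: item 9 where the PHQ-9 is asked, the telephone risk procedure, and reports that participants initiate. And the call loses nothing compared with no call, while participants who are never reached lack the same answer and are likely to be far more numerous.

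A reader might infer more than this. One inference is that 7.4 and SAP 3.9 also restrict the call's content; they do not. Another is that the omission biases the comparison between arms; nothing in the documents suggests that telephone completion differs by arm. A third is that leaving out the AD-SUS hospital items is an error; it is a reasonable trade-off, although it narrows what the call can recover.

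**Conclusion.** The inconsistency is real and minor. Protocol 7 and 7.7 confine the call to the primary outcome measures, and 9.3 and 16.4 require adverse-event collection at each follow-up. As written, the SAE question is not asked by telephone, and item 9 does not replace it for the 12-month counts in SAP 6.10. The gain from asking it is 2 months of cover at a 3-month call and 3 months at a 12-month call, given an online 1-month follow-up, for a number of people that the documents do not allow one to estimate and that the SAP expects to be small. No treatment estimate is shown to be affected.

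**What to change.** In Protocol 7 and 7.7, replace the limit with: the primary outcome measures, followed by the SAE question of section 16.5. Ask it once the outcomes are recorded, with the online wording and look-back. Leave out the 16.5 questions on app problems and on whether taking part made the person feel better or worse, because the answers could reveal the allocation. Do not require the AD-SUS items.

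In SAP 6.10, report by arm, visit and mode how many participants answered the SAE question, and treat those not asked as missing, not event-free. Mode is available because SAP 3.9 already has telephone data marked as such.

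The cost is a protocol amendment with sponsor and ethics approval (Protocol 13.10), a SAP revision (SAP 1.7) and a slightly longer call. A small unblinding risk remains, since the SAE question lists trial participation among the possible causes. The reminder in Protocol 7.4 not to disclose the app version should be kept. For at least 1903 of the original 2141 participants the 3-month calls cannot be recovered, so the change mainly helps 12-month calls and the replenishment sample. Reporting by visit and mode makes the earlier gap visible.
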